---

### Summary of Changes from Previous Version:

Affected Section(s)	Summary of Revisions Made	Rationale
Title	Improve clarity of terms	
Section 1	Clarification fo Schema	
Section 2	Expansion of study rational	
Section 2	Expanded discussion of risks/benefits	
Section 4, 6	Optimisation of drug dosing	
Section 5	Additional Exclusion Criteria	

## STATEMENT OF COMPLIANCE

The trial will be carried out in accordance with National Health and Medical Research Council (NHMRC), Therapeutic Goods Administration (TGA) guidelines and International Conference on Harmonisation Good Clinical Practice (ICH GCP) and the following:

- Ethics approval from the Women's and Children's Hospital, Adelaide, Australia
- NHMRC Trial Registration
- ANZCA Clinical Trials Network Registration

The protocol, informed consent form(s), recruitment materials, and all participant materials will be submitted to the Human Ethics Committee for review and approval. Approval of both the protocol and the consent form must be obtained before any participant is enrolled. Any amendment to the protocol will require review and approval by the Ethics Committee before the changes are implemented to the study. In addition, all changes to the consent form will be Ethics Committee approved; a determination will be made regarding whether a new consent needs to be obtained from participants who provided consent, using a previously approved consent form.

[figure not shown]
## 1. PROTOCOL SUMMARY

### 1.1. SYNOPSIS

Title:	Correction of preoperative iron deficiency in children undergoing elective spinal fusion. A Randomised control trial of intravenous iron (ferric carboxymaltose) vs. oral iron therapy.	
Study Description:	
This study aims to compare the efficacy of intravenous (IV) carboxymaltose iron infusion compared with oral iron therapy (ferrous fumarate or ferrous sulphate) in the correction of preoperative iron deficiency for paediatric patients presenting for spinal fusion surgery.
 
Preoperative iron replacement using intravenous iron infusions have been demonstrated to be effective in adult patients presenting for major surgery. This research has not been conducted in perioperative paediatric patients. We hope to address the clinical question of whether to prescribe oral iron or intravenous iron therapy when patients are found to be iron deficient prior to imminent surgery (within 6 weeks).
 
We aim to demonstrate the superiority of preoperative IV ferric carboxymaltose iron infusions over oral iron therapy in paediatric surgical patients. We expect to see a decrease in the incidence of severe anaemia at discharge, lower rates of transfusion, improved recovery and faster resolution of post operative anaemia.
	
Objectives:	Primary Objective: To investigate the incidence of severe anaemia (Hb < 100g/L) after spinal fusion surgery following administration of either intravenous ferric carboxymaltose or oral iron therapy.	
Endpoints:	Primary Endpoint: Incidence of Hb <100g/L at time of discharge from hospital or one week post operatively (whichever is shorter).	Secondary Endpoints: Incidence of blood transfusion, length of stay, haemoglobin concentration and incidence of anaemia (Hb <120g/L) at 3-5 weeks post operatively, and haemoglobin concentration and incidence of anaemia (Hb <120g/L) and iron studies at 6-12 weeks post operatively, and quality of functional recovery from surgery as measured by the SRS 30.
Study Population:	34 (17 in each arm) ASA 1 and 2 patients under the age of 18 years who present for elective spinal fusion for adolescent idiopathic scoliosis at the Women's and Children's Hospital, Adelaide Australia.	
Phase:	Phase III trial - investigating effectiveness of ferric carboxymaltose in a paediatric surgical population.	
Description of Sites/ Facilities Enrolling Participants:	This study will be conducted at the Women's and Children's Hospital in Adelaide, Australia. This is a 314 bed tertiary level paediatric hospital.	

Description of Study Intervention:	
Patients who are found to be iron deficient on preoperative screening will be randomised to receive either oral iron therapy (control) or intravenous (IV) ferric carboxymaltose iron (intervention).
 
The dose of oral iron therapy will be 3-6mg/kg/day of elemental iron in the form of Ferrous Sulphate liquid or Ferrous Fumarate tablets administered for at least 3-5 weeks preoperatively. The dose of IV ferric carboxymaltose will be determined based on patient weight and haemoglobin (see below) this will be administered 3-5 weeks preoperatively.

Study Duration:	Estimated 36 months.
Participant Duration:	5 months

1.2. SCHEMA

**1.3. SCHEDULE OF ACTIVITIES (SOA)**

Procedures	Enrolment/ Visit 1, Day -42 (+/- 14 days)	Group identification, Day -35 (+/- 14 days)	Study Visit 2, Day -28 (+/- 7 days)	Day Before Surgery Day -1	Day of Surgery Day 0	In hospital Days 1-5	Discharge Day 5 (+/- 2days)	Study Visit 3 Day 21 (+/- 7 days)	Final Study Visit 4 Day 63 (+/- 14 days )
Informed consent	X								
Demographics	X								
Medical history	X								
Baseline screening bloods	X								
Interpretation of bloods		X							
Randomization		X							
Administer study intervention - Intravenous iron therapy (IV arm only)			X						
Administer study intervention - Oral iron therapy (Oral arm only)		X-----X							
Vital signs	X		X		X	X	X		X
Height	X								X
Weight	X								X
SRS 30 Questionnaire	X								X
Full Blood Exam	X				X	X	X	X	X
Iron Studies	X				X				X
Electrolytes (“ELC”)	X				X				X
Vitamin D Level	X								
Surgical data - ASA, spinal levels, blood loss, cell salvage volume					X				
Transfusion volume					X	X	X		
Oral Iron Compliance Questionnaire						X			
Adverse event review and evaluation	X	X-----X							X
Data Entry	X	X	X		X	X	X	X	X

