### 3. OBJECTIVES AND ENDPOINTS

OBJECTIVES	ENDPOINTS	JUSTIFICATION FOR ENDPOINTS
Primary		
To compare the efficacy of two forms of iron replacement therapy in the prevention of severe anaemia at discharge from hospital.	The primary endpoint is the incidence of severe anaemia (haemoglobin <100g/L) the time of discharge from hospital (or one week postoperatively, whichever one is sooner).	Severe post operative anaemia is a clinically relevant method to measure the impact of preoperative iron therapy. It is simple to measure and is not subjective to bias.
Secondary		
To compare the postoperative effect of preoperative correction of iron deficiency with two different forms of iron replacement.	
 
- Incidence of blood transfusion
 
- Length of stay
 
- 3-5 weeks postoperatively                             
 
- Haemoglobin concentration
 
- Incidence of anaemia (Hb<120g/L)
 
 
 
- 6-12 weeks postoperatively                             
 
- Haemoglobin concentration
 
- Incidence of anaemia (Hb <120g/L)
 
- Iron studies
 
- Quality of functional recovery from surgery as measured by the SRS 30.
 
 
 
	These endpoints are clinically relevant markers of recovery from surgery. Post operative recovery of haemoglobin concentration is a clinically important effect of adequate iron stores.

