#### Prior to discharge - Day 5 (+/-2 days) Postoperative

Patients will undergo routine:

- Measure of vital signs
- Collection of blood for Full Blood Exam

- This will occur one day prior to discharge or at 7 days postoperatively (whichever is sooner)
- Documentation of any transfusion
- Patients will be asked to complete their oral iron therapy compliance questionnaire

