#### Final Study visit 12 weeks (+/- 4 weeks) Postoperatively

Patients will present to Women's and Children's hospital for routine follow up by their surgeon. At this appointment we will:

- Measure vitals
- Document height and weight
- Collection blood for Full Blood Exam, Iron Studies and Electrolytes including Calcium, Magnesium and Phosphate ("ELC")
- Collect follow up SRS 30 Questionnaire

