## 9. STATISTICAL CONSIDERATIONS

### 9.1. STATISTICAL HYPOTHESES

- Primary Efficacy Endpoint(s):
  - Incidence of severe anaemia (Hb <100g/L) at time of discharge from hospital or 7 days postoperatively (whichever is sooner)
  - This trial is designed to demonstrate superiority of IV iron therapy over traditional oral iron therapy.
- Secondary Efficacy Endpoint(s):
  - Incidence of blood transfusion
  - Length of stay
  - Haemoglobin concentration and incidence of anaemia (Hb <120g/L) at 3 weeks postoperatively
  - Haemoglobin concentration and incidence of anaemia (Hb <120g/L) and incidence of iron deficiency (ferritin <30mcg/L) at 9 weeks postoperatively
  - Quality of functional recovery from surgery as measured by the SRS 30 at 9 weeks postoperatively

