**0-7 days postoperative**

Date of discharge: \_\_\_/\_\_\_/\_\_\_

	Day 1	Day 2	Day 3	Day 4	Day 5	Day 6	Day 7
Haemoglobin							
Transfused (yes/no)							
Observations stable (yes/no)							
Phosphate Level							
Day of discharge							

**Please complete a Full Blood Examination on Day 1-2 and Day 5-7 and at least one test of Electrolytes including Calcium Magnesium and Phosphate "ELC" prior to discharge**

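### Three postoperative timing rules conflict: the early haemoglobin window, the final-visit window, and the ward form's instruction for the primary blood sample

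*Protocol*

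**What the plan says.** **Early follow-up.** Section 3 and the Synopsis place haemoglobin and the incidence of anaemia at "3-5 weeks postoperatively". The Schedule (Section 1.3) has "Study Visit 3 Day 21 (+/- 7 days". Section 8.1 puts the wound-review visit at three weeks with one week either side, and the postoperative sheet in Appendix D labels the column as weeks 2 to 4. Section 9.1 names week 3 without a window.

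**Late follow-up.** Section 3, the Synopsis and the Appendix D sheet give weeks 6 to 12. The Schedule has "Final Study Visit 4 Day 63 (+/- 14 days". Section 8.1 has "Final Study visit 12 weeks (+/- 4 weeks) Postoperatively". Section 4.1 ends follow-up at 12 weeks, and Section 5.3 also places the final investigations there. Section 9.1 lists "incidence of iron deficiency (ferritin <30mcg/L) at 9 weeks postoperatively".

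**Primary sample.** The Synopsis defines the endpoint as "Incidence of Hb <100g/L at time of discharge from hospital or one week post operatively (whichever is shorter". Section 8.1 says of the blood count: "This will occur one day prior to discharge or at 7 days postoperatively (whichever is sooner". The Schedule puts discharge at Day 5, plus or minus 2 days, and marks a full blood examination (FBE) both for the in-hospital days and at discharge. The in-patient sheet in Appendix D carries the printed instruction "Please complete a Full Blood Examination on Day 1-2 and Day 5-7".

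**The concern.** Each endpoint needs one collection window, and the instructions that staff work from have to produce a sample inside it. Here the early endpoint window and the collection window overlap only in part. The final visit has two collection windows that share only some days. The form used on the ward does not ask for the primary sample on the day that Section 8.1 specifies.

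For the two follow-up visits, a patient seen exactly as instructed can have a value that does not belong to the endpoint as defined. Someone must then decide afterwards whether to keep it. For the primary endpoint, the risk is a sample that is never drawn or is drawn early, which no later analysis rule can repair. With 17 children per arm, one lost primary value is 1/17 = 5.9% of an arm.

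**Working it through.** All windows are converted to postoperative days at 7 days per week, with both ends included.

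**1. Early haemoglobin and anaemia endpoint**

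- Endpoint (Synopsis, Section 3): 3 × 7 to 5 × 7 = Days 21-35.
- Collection (Schedule): 21 − 7 to 21 + 7 = Days 14-28, which is 15 permitted days. Section 8.1 and the Appendix D sheet give the same days.
- Overlap: Days 21-28 = 8 days.
- Permitted but outside the endpoint: Days 14-20 = 7 of 15 days (47%).
- In the endpoint but never sampled on schedule: Days 29-35 = 7 days.

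No collection instruction matches the endpoint, so this conflict arises whichever one staff follow.

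**2. Final visit**

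| Source | Days | Relation to the endpoint window (Days 42-84) |
|---|---|---|
| Section 3, Synopsis, Appendix D sheet: weeks 6-12 | 42-84 | identical |
| Schedule: 63 ± 14 | 49-77 | all 29 days inside |
| Section 8.1: 12 ± 4 weeks | 56-112 | 29 of 57 days inside (56-84); 28 of 57 outside (85-112), 49% |

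Section 8.1 and the Schedule share only Days 56-77, or 22 days. The other 35 of the 57 days in Section 8.1 (61%) fall outside the Schedule. Section 8.1 also runs 112 − 84 = 28 days past the end of follow-up in Section 4.1.

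**3. Primary sample**

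Under Section 8.1, the sample day for discharge on day d is the smaller of d − 1 and 7. The sheet's instruction covers Days 1-2 and 5-7.

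| Discharge day | Section 8.1 sample day | Day covered by the sheet's instruction? |
|---|---|---|
| 3 | 2 | yes, if the first count is taken on Day 2 rather than Day 1 |
| 4 | 3 | no |
| 5 | 4 | no |
| 6 | 5 | yes |
| 7 | 6 | yes |
| 8 or later | 7 | yes |

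The Schedule allows discharge on Days 3 to 7. A child who leaves on Day 3 or 4 cannot have the sheet's Day 5-7 count in hospital, so the sheet alone yields only a Day 1-2 value. For Day 3 that value can still satisfy Section 8.1; for Day 4 it cannot. A child who leaves on Day 5 could have a count that day, but not on the day Section 8.1 names.

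**The case against.** The strongest reply is that the protocol body already secures most of this.

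- **Final visit.** The Schedule's window lies wholly inside weeks 6 to 12, and the data sheet matches the endpoint. Section 8.1 is the one outlier. This stands. A reader might infer that on-schedule bloods fall outside the endpoint at both follow-up visits; the documents support that for the early visit only.
- **Section 9.1.** Weeks 3 and 9 are the centres of the Schedule's Day 21 and Day 63 visits. Naming a visit by its target day does not contradict its tolerance. This stands, and Section 9.1 is not counted here as a conflict.
- **Primary sample.** Section 8.1 and the Schedule both require a count before discharge, and the sheet has a haemoglobin cell for each of Days 1 to 7. The sample is therefore lost or mistimed only where staff follow the printed line and not the protocol. This limits the point but does not remove it, because that line is an explicit instruction on the data form and asks for different days.
- **Analysis windows can be set in a statistical analysis plan.** That is true of which visits to accept. It does not cover which collection window the site applies, or a sample that was not drawn.
- **Both arms share the same windows.** This stands: the mismatch builds in no difference in timing between arms.

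Three stronger readings are tempting and are not supported. The percentages above are shares of permitted days; the protocol gives no distribution of visit or discharge days, so they do not estimate shares of patients. A reader might also infer that missing primary samples would be related to outcome because they arise in children who go home early; nothing in the documents shows that. Finally, adjusting the haemoglobin analyses for the actual postoperative day is not a sound repair. That day is fixed after randomisation, and for the discharge sample it is tied to length of stay, which is itself a secondary endpoint that treatment may affect.

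**Conclusion.** The point holds as three contradictions in the current text.

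1. The early endpoint is defined on Days 21-35 and collected on Days 14-28. Seven of the 15 permitted days give a compliant value outside the endpoint.
2. The Section 8.1 final visit (Days 56-112) conflicts with the Schedule, with the weeks 6 to 12 endpoint and with the end of follow-up in Section 4.1. It is the only window that runs past the endpoint, on Days 85-112.
3. The in-patient sheet does not request the primary sample that Section 8.1 requires for discharge on Day 4 or Day 5. A child discharged on Day 3 or 4 has only a Day 1-2 count if the sheet alone is followed.

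The first two affect secondary endpoints. The third can affect the primary endpoint, and it depends on staff following the form. How many patients would be affected cannot be derived from the protocol. The sample size calculation is not affected. The conversion rests only on 7-day weeks and inclusive window limits.

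**What to change.** - **Early endpoint.** Define it by the window actually collected, weeks 2 to 4, in the Synopsis, Section 3 and Section 9.1. The Appendix D column already says this and should stay in line.
- **Final visit.** Reconcile the Section 8.1 window with the Schedule and the weeks 6 to 12 endpoint, so that one window appears in the Synopsis, Sections 1.3, 3, 8.1 and 9.1, and Appendix D. It should also agree with the end of follow-up in Section 4.1.
- **In-patient sheet.** Replace the fixed Day 5-7 request with a second FBE before discharge, timed as in Section 8.1, or on Day 7 if the child is still in hospital.

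The cost is an editorial amendment, which needs ethics committee approval under the Statement of Compliance, and one corrected form. It adds no visit, and no blood test beyond those Section 8.1 already requires.

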## 2. INTRODUCTION

### 2.1. STUDY RATIONALE

Posterior spinal fusion is considered major elective surgery which is associated with significant intra operative blood loss and post operative anaemia. A retrospective audit at our institution in 2016 has demonstrated that a significant number of patients were presenting for surgery with anaemia (Hb <120g/L) and over 60% of all spinal fusion patients were being discharged from hospital with severe anaemia (Hb <100g/L).

While preoperative optimisation of red cell mass is considered standard practice in the adult perioperative setting there have been few studies to assess its application in paediatric surgery. At the present time there is little preoperative screening in place for systemically well paediatric patients. Until recently patients at our institution were not undergoing routine screening bloods until the night before surgery preventing any preoperative treatment of iron deficiency or anaemia. The perioperative patient who is found to be iron deficient presents a unique challenge to surgeons and anaesthetists who are faced with balancing the desire to provide the best preoperative optimisation without delaying surgery whenever possible. Therefore this study seeks to answer the valuable question of how to best optimise our patient's iron stores in the limited pre-operative period. We aim to determine whether oral iron or intravenous iron is more effective where there is only 4-6 weeks available to achieve adequate replacement of the patients iron stores.

This study aims to assess the efficacy of preoperative screening and treatment of iron deficiency with either oral iron (ferrous sulphate liquid or ferrous fumarate tablets) or intravenous ferric carboxymaltose iron therapy in the paediatric perioperative patient.

### 2.2. BACKGROUND

Posterior spinal fusion for correction of adolescent idiopathic scoliosis is a major elective surgery which is associated with significant intra-operative blood loss and postoperative anaemia. The National Blood Authority describes three pillars of perioperative blood management (preoperative optimisation, minimisation of intra-operative blood loss and tolerance of postoperative anaemia) which, when utilised appropriately aim to reduce the burden of perioperative blood transfusion and postoperative anaemia.

Over the last 15 years there have been significant advances in surgical and anaesthetic techniques which, along with the use of intra-operative cell salvage, have drastically reduced the requirement for perioperative blood transfusion. However, these paediatric patients are still vulnerable to high volumes of intra-operative blood loss resulting in significant postoperative anaemia.

In a recent (2016) retrospective audit at our hospital we have found that 18% of patients presenting for posterior spinal fusion are anaemic (Hb <120g/L) preoperatively with up to 30% demonstrating blood films consistent with iron deficiency. These patients had an average intra-operative blood loss of over 500mL. At discharge 68% of patients were found to have severe anaemia (Hb <100g/L). Iron deficiency is the largest contributing factor to anaemia in all paediatric age groups. This audit demonstrated a need for further study into the effects of thorough preoperative screening and optimisation of iron and red cell stores in the paediatric surgical population.

There are two options for replacement of iron stores to correct iron deficiency. The traditional first line therapy is oral iron supplementation followed by intravenous iron therapy in those patients who fail to respond to oral iron. However, oral iron therapy takes time to work and is often poorly tolerated due to gastrointestinal side effects and for these reasons is commonly felt to not be a viable option in the preoperative patient who requires optimisation in a matter of weeks rather than months. Traditional intravenous iron preparations required up to 6 hours for safe infusion time which was a significant deterrent for many paediatric patients. However, with the new formulation of IV ferric carboxymaltose only requiring 15 minutes of infusion time and an improved risk profile, the balance of oral vs IV iron therapy is due to be revisited. Intravenous ferric carboxymaltose formulation has been demonstrated to be safe and effective in the treatment of iron deficiency due to inflammatory bowel disease in paediatric patients but its efficacy has not been trialed in the perioperative paediatric population.

This project aims to improve perioperative blood management through optimising preoperative haemoglobin and iron stores. There is significant data supporting the use of preoperative iron infusions in adult surgical patients, however this research has not been conducted in paediatric patients presenting for major surgery. This trial aims to assess the efficacy of preoperative intravenous (IV) ferric carboxymaltose iron infusion compared with traditional treatment of iron deficiency with oral iron therapy (ferrous sulphate liquid or ferrous fumarate tablets). If IV ferric carboxymaltose is found to be superior to oral iron therapy then it maybe that the additional cost and risk of the IV formulation can be justified for the management of preoperative iron deficiency in paediatric patients. If it is found that oral iron is as effective as IV iron then this information will help to change medical opinion of the role of oral iron in the preoperative setting.

We expect that by adequately correcting iron deficiency and thus improving the patients preoperative haemoglobin and iron stores we will see a decreased rate of severe anaemia at discharge. We also hope to see an improved recovery from surgery as is demonstrated in a decreased rate of blood transfusion, shorter length of stay, improved SRS 30 (Scoliosis Patient Questionnaire Version 30), and decreased incidence of anaemia and iron deficiency at 6-12 weeks post operatively.

## 2.3. RISK/BENEFIT ASSESSMENT

### 2.3.1. KNOWN POTENTIAL RISKS

#### IV Ferric Carboxymaltose

As discussed in the NPS Medicinewise RADAR “Ferric carboxymaltose (Ferinject) for iron-deficiency anaemia” (<https://www.nps.org.au/radar/articles/ferric-carboxymaltose-ferinject-for-iron-deficiency-anaemia>)

Pooled safety information for ferric carboxymaltose (FCM) comprising the total short-term phase II/III database of 20 trials has recently been published, and is the largest database reported thus far for any IV iron formulation.

In this set of patients administered FCM (n = 5799), treatment-related side effects that occurred in more than 1% of the group included:

- nausea (3.1%),
- hypophosphataemia (1.9%),
  - Hypophosphataemia occurs but is transient

- An increased risk of transient asymptomatic hypophosphataemia has been observed in trials of FCM and appears to occur more often in association with FCM than with other iron preparations.
- Severe cases with clinical sequelae are rare. Patients at increased risk of this adverse event include those with a concomitant disorder of phosphate homeostasis such as hyperparathyroidism or vitamin D deficiency.
- In our study we will exclude any patients who are found to have hypophosphataemia on initial screening and we will monitor phosphate levels during the followup period. We will screen for vitamin D deficiency and hyperparathyroidism by measuring the vitamin D levels and serum calcium levels and any patient with elevated calcium will be referred for further testing of parathyroid hormone levels.
- injection-site reactions(1.6%),
- headache (1.4%),
- hypertension (1.3%),
  - In recently completed FCM trials, protocol-defined hypertensive events have been reported to occur more frequently among FCM-treated patients compared with those receiving other iron preparations (oral and IV). Most of these events occurred during the observation period following iron injection/infusion.
  - Monitor patients closely, especially when large single doses > 200 mg iron are administered.
- dizziness (1.2%).
- anaphylaxis
  - Cardiopulmonary equipment must be available for managing anaphylaxis before administering FCM
  - All IV iron preparations carry a small risk of causing life-threatening hypersensitivity reactions.
  - In the pooled database of short-term phase II/III trials the rate of hypersensitivity or allergic reactions potentially due to FCM treatment was 0.9% (n = 51/5799) for FCM compared with 0.8% (n = 42/5272) for all comparators and 1.5% for other IV iron preparations (n = 37/2439).
  - Patients should be monitored during and immediately after infusion.
- Risk of permanent skin tattooing if FCM is injected into a dislodged cannula.
  - FCM should be administered either by slow manual push or a free hanging bag. Use of syringe drivers and pumps increases the risk of an unrecognised tissue cannula.

As per the manufacturer's guidelines ferric carboxymaltose is currently recommended for patients 14 years of age and older. However multiple studies have evaluated its use in the paediatric population. It has been demonstrated to be safe and effective in the treatment of iron deficiency due to inflammatory bowel disease in paediatric patients but its efficacy has not been trialed in the perioperative paediatric population. There are no known additional risks in children as compared to adults but there may be further unknown risks.

